10.1.7. Source Documents

Source documents provide evidence for the existence of the participant and substantiate the integrity of the data collected. Source documents are filed at the investigator site.

Data reported on the CRF or entered in the eCRF that are from source documents must be consistent with the source documents or the discrepancies must be explained. The investigator may need to request previous medical records or transfer records, depending on the study. Also, current medical records must be available.

Definition of what constitutes source data can be found in the study monitoring plan.

Description of the use of computerized system is documented in the Data Management Plan.

10.1.8. Study and Site Start and Closure

The study start date is the date on which the clinical study will be open for recruitment of participants.

The first act of recruitment is the date of the first participant's first visit and will be the study start date.

The sponsor designee reserves the right to close the study site or terminate the study at any time for any reason at the sole discretion of the sponsor. Study sites will be closed upon study completion. A study site is considered closed when all required documents and study supplies have been collected and a study-site closure visit has been performed.

The investigator may initiate study-site closure at any time upon notification to the sponsor or designee/CRO if requested to do so by the responsible IRB/EC or if such termination is required to protect the health of study participants.

Reasons for the early closure of a study site by the sponsor may include but are not limited to:

- Failure of the investigator to comply with the protocol, the requirements of the IRB/EC or local health authorities, the sponsor's procedures, or GCP guidelines.

- Inadequate recruitment of participants by the investigator.
- Discontinuation of further study intervention development.

If the study is prematurely terminated or suspended, the sponsor shall promptly inform the investigators, the ECs/IRBs, the regulatory authorities, and any CRO(s) used in the study of the reason for termination or suspension, as specified by the applicable regulatory requirements. The investigator shall promptly inform the participant and should assure appropriate participant therapy and/or follow-up.

Study termination is also provided for in the clinical study agreement. If there is any conflict between the contract and this protocol, the contract will control as to termination rights.

10.1.9. Publication Policy

The results of this study may be published or presented at scientific meetings by the investigator after publication of the overall study results or 1 year after the end of the study (or study termination), whichever comes first.

The investigator agrees to refer to the primary publication in any subsequent publications such as secondary manuscripts and submits all manuscripts or abstracts to the sponsor 30 days before submission. This allows the sponsor to protect proprietary information and to provide comments and the investigator will, on request, remove any previously undisclosed confidential information before disclosure, except for any study- or Pfizer intervention-related information necessary for the appropriate scientific presentation or understanding of the study results.

For all publications relating to the study, the investigator will comply with recognized ethical standards concerning publications and authorship, including those established by the International Committee of Medical Journal Editors.

The sponsor will comply with the requirements for publication of the overall study results covering all investigator sites. In accordance with standard editorial and ethical practice, the sponsor will support publication of multicenter studies only in their entirety and not as individual site data. In this case, a coordinating investigator will be designated by mutual agreement.

Authorship of publications for the overall study results will be determined by mutual agreement and in line with International Committee of Medical Journal Editors authorship requirements.

If publication is addressed in the clinical study agreement, the publication policy set out in this section will not apply.

10.1.10. Sponsor's Qualified Medical Personnel

The contact information for the sponsor's appropriately qualified medical personnel for the study is documented in the study contact list located in the SToD system.

To facilitate access to appropriately qualified medical personnel on study-related medical questions or problems, participants are provided with a contact card at the time of informed consent. The contact card contains, at a minimum, protocol and study intervention identifiers, participant numbers, contact information for the investigator site, and contact details for a contact center in the event that the investigator site staff cannot be reached to provide advice on a medical question or problem originating from another healthcare professional not involved in the participant's participation in the study. The contact number can also be used by investigator staff if they are seeking advice on medical questions or problems; however, it should be used only in the event that the established communication pathways between the investigator site and the study team are not available. It is therefore intended to augment, but not replace, the established communication pathways between the investigator site and the study team for advice on medical questions or problems that may arise during the study. The contact number is not intended for use by the participant directly, and if a participant calls that number, he or she will be directed back to the investigator site.

10.2. Appendix 2: Clinical Laboratory Tests

The following safety laboratory tests will be performed at times defined in the **SoA** section of this protocol. Additional laboratory results may be reported on these samples as a result of the method of analysis or the type of analyzer used by the clinical laboratory, or as derived from calculated values. These additional tests would not require additional collection of blood. Unscheduled clinical laboratory measurements may be obtained at any time during the study to assess any perceived safety issues.

Table 10. Protocol-Required Safety Laboratory Assessments

Hematology	Chemistry	Urinalysis	Other
Hemoglobin	BUN	pH	At screening only:
Hematocrit	serum creatinine (and eGFR using Cockcroft-Gault)	Glucose (qual)	
 • FSH^b • Pregnancy test (β-hCG)^c
RBC count		Protein (qual)	
MCV		Blood (qual)	
MCH	Glucose	Ketones	At timepoints in SoA:
MCHC	Calcium	Nitrites	
 • Coagulation 
 • D-dimer • PT/INR • aPTT • Fibrinogen
Platelet count	Sodium	Leukocyte esterase	
WBC count	Potassium	Urobilinogen	
Total neutrophils (Abs)	Chloride	Urine bilirubin	
Eosinophils (Abs)	Total	Microscopy ^a	
Monocytes (Abs)	CO ₂ (bicarbonate)		
Basophils (Abs)	AST, ALT		
Lymphocytes (Abs)	Phosphorus		
	Total bilirubin		
	Alkaline phosphatase		
	Uric acid		
	Albumin		
	Total protein		
	Lipid panel (Part 2 only)		

- a. Only if urine dipstick is positive for blood, protein, nitrites, or leukocyte esterase.
- b. For confirmation of postmenopausal status only.
- c. Local urine testing will be standard for the protocol unless serum testing is required by local regulation or IRB/EC. Serum or urine β -hCG for female participants of childbearing potential.

Investigators must document their review of each laboratory safety report.

10.3. Appendix 3: Adverse Events: Definitions and Procedures for Recording, Evaluating, Follow-up, and Reporting

10.3.1. Definition of AE

AE Definition

• An AE is any untoward medical occurrence in a patient or clinical study participant, temporally associated with the use of study intervention, whether or not considered related to the study intervention.• NOTE: An AE can therefore be any unfavorable and unintended sign (including an abnormal laboratory finding), symptom, or disease (new or exacerbated) temporally associated with the use of study intervention.

Events Meeting the AE Definition

• Any abnormal laboratory test results (hematology, clinical chemistry, or urinalysis) or other safety assessments (eg, ECG, radiological scans, vital sign measurements), including those that worsen from baseline, considered clinically significant in the medical and scientific judgment of the investigator Any abnormal laboratory test results that meet any of the conditions below must be recorded as an AE:
• Is associated with accompanying symptoms.• Requires additional diagnostic testing or medical/surgical intervention.• Leads to a change in study dosing (outside of any protocol-specified dose adjustments) or discontinuation from the study, significant additional concomitant drug treatment, or other therapy.• Exacerbation of a chronic or intermittent preexisting condition including either an increase in frequency and/or intensity of the condition.• New conditions detected or diagnosed after study intervention administration even though it may have been present before the start of the study.• Signs, symptoms, or the clinical sequelae of a suspected drug-drug interaction.• Signs, symptoms, or the clinical sequelae of a suspected overdose of either study intervention or a concomitant medication. Overdose per se will not be reported as an AE/SAE unless it is an intentional overdose taken with possible suicidal/self-harming intent. Such overdoses should be reported regardless of sequelae.

Events NOT Meeting the AE Definition

- Any clinically significant abnormal laboratory findings or other abnormal safety assessments which are associated with the underlying disease, unless judged by the investigator to be more severe than expected for the participant's condition.
- The disease/disorder being studied or expected progression, signs, or symptoms of the disease/disorder being studied, unless more severe than expected for the participant's condition.
- Medical or surgical procedure (eg, endoscopy, appendectomy): the condition that leads to the procedure is the AE.
- Situations in which an untoward medical occurrence did not occur (social and/or convenience admission to a hospital).
- Anticipated day-to-day fluctuations of preexisting disease(s) or condition(s) present or detected at the start of the study that do not worsen.

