2.2. Background

Disease Overview

In December 2019, COVID-19 was identified as a new, potentially fatal, respiratory infection caused by the novel coronavirus, SARS-CoV-2. The WHO declared COVID-19 a Public Health Emergency of International Concern on 20 January 2020 and further characterized the disease outbreak as a pandemic on 11 March 2020.¹

COVID-19 manifests as a wide range of illness, from asymptomatic infection to severe pneumonia, ARDS and death. While the majority of cases (approximately 80%) are asymptomatic or mild,² patients who are hospitalized with COVID-19 may have significant morbidity and mortality,^{3,4} and are at increased risk of developing complications such as severe inflammation associated with elevations in pro-inflammatory cytokines, ARDS, acute cardiac injury, thromboembolic events, hypercoagulability, and/or kidney injury.⁵⁻⁹

Current Treatment Options

As of December 2020, vaccines are not yet widely available to prevent infection with SARS-CoV-2 and aside from symptomatic and/or supportive treatments there are few drugs approved and available to treat COVID-19. As of June, 2020, only 1 anti-viral drug with activity against SARS-CoV-2, Remdesivir, an RNA polymerase inhibitor, has shown clinical benefit in hospitalized patients with COVID-19.¹⁰ While additional data from studies of Remdesivir and other drugs are becoming available, published preliminary reports suggest that Remdesivir may not be sufficient as monotherapy in all subsets of patients across the spectrum of disease.¹⁰ Furthermore, Remdesivir is only available on a limited basis, through emergency use authorization in the US,¹¹ authorization for compassionate use in the EU,¹² and approved in a small number of countries.¹³⁻¹⁵

The FDA has issued EUA to 2 monoclonal antibodies, bamlanivimab and the combination casirivimab plus imdevimab, the drug baricitinab, in combination with remdesivir, and convalescent plasma for the treatment of COVID-19. The use of monoclonal antibodies is limited to the outpatient setting in patients at high risk of progressing to severe disease and/or hospitalization. At the time of the most recent update to the COVID-19 Treatment Guidelines Panel (03 December 2020), the Panel did not believe there was sufficient data to recommend any of these 4 therapeutics as part of the standard of care.

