2.2.2.1. Study C4611007 - Ongoing

This is the second clinical administration with PF-07304814, but first in healthy adult participants. This is a Phase 1, randomized, double-blind, sponsor open (ie, participant blind, investigator blind and sponsor open), placebo-controlled SAD study, with ongoing review of safety, tolerability, and PK.

There are 2 interleaving cohorts with a total of approximately 16 participants (approximately 8 participants in each cohort), with 2-period cross-over in each cohort. For each period, approximately 6 participants will have received a single dose of PF-07304814 administered as a 24h continuous IV infusion, and approximately 2 participants will have received placebo. Each participant may have received either a single dose of PF-07304814 or a placebo during each period.

The nominal doses of PF-07304814 are 50 mg, 150 mg, 500 mg, and 700 mg for a 24h continuous infusion. In addition to standard safety assessments, hsCRP, D-dimer, and coagulation panel (aPTT, PTT) are monitored to evaluate any potential pro-inflammatory or hypercoagulable effect of study intervention.

The study began in October 2020, and at the time of the data cutoff date 21 November 2020, safety data from last planned safety labs (Day 5) from the last participant was reviewed. There were 20 TEAEs reported by 12 participants. All of the TEAEs were categorized as mild in severity. One AE of injection site pain, reported as mild in severity, was considered treatment related by the investigator. For the description of each AEs please refer to the IB (December 2020). There were no deaths, serious AEs (SAEs), severe AEs, or discontinuations due to AEs during the study.

There were no individual laboratory abnormalities assessed as clinically significant by the investigator. Across the treatment groups there were no clinically significant changes in the inflammatory marker, hs-CRP. Tests evaluating the coagulation system, aPTT, PT, fibrinogen and D-dimer, were similarly without clinically significant changes over time. No participant developed a value that was clinically significantly elevated or outside the normal range. Overall, there was no evidence of a pro-inflammatory effect clinically or based on laboratory results, at all dose levels.

Preliminary pharmacokinetic (PK) data following single dose 24h continuous IV infusion at 50, 150, 500 and 700 mg are included in this update with a data cut-off date of 21 November 2020.

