8.3.6. Cardiovascular and Death Events

Not applicable.

8.3.7. Disease Related Events and/or Disease Related Outcomes Not Qualifying as AEs or SAEs

Not applicable.

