10.3.2. Definition of SAE

If an event is not an AE per definition above, then it cannot be an SAE even if serious conditions are met (eg, hospitalization for signs/symptoms of the disease under study, death due to progression of disease).

An SAE is defined as any untoward medical occurrence that, at any dose:
a. Results in death
b. Is life-threatening
The term "life-threatening" in the definition of "serious" refers to an event in which the participant was at risk of death at the time of the event. It does not refer to an event that hypothetically might have caused death if it were more severe.
c. Requires inpatient hospitalization or prolongation of existing hospitalization
In general, hospitalization signifies that the participant has been detained (usually involving at least an overnight stay) at the hospital or emergency ward for observation and/or treatment that would not have been appropriate in the physician's office or outpatient setting. Complications that occur during hospitalization are AEs. If a complication prolongs hospitalization or fulfills any other serious criteria, the event is serious. When in doubt as to whether "hospitalization" occurred or was necessary, the AE

should be considered serious.

Hospitalization for elective treatment of a preexisting condition that did not worsen from baseline is not considered an AE.

d. Results in persistent disability/incapacity

- The term disability means a substantial disruption of a person's ability to conduct normal life functions.
- This definition is not intended to include experiences of relatively minor medical significance such as uncomplicated headache, nausea, vomiting, diarrhea, influenza, and accidental trauma (eg, sprained ankle) which may interfere with or prevent everyday life functions but do not constitute a substantial disruption.

e. Is a congenital anomaly/birth defect

f. Other situations:

- Medical or scientific judgment should be exercised in deciding whether SAE reporting is appropriate in other situations such as important medical events that may not be immediately life-threatening or result in death or hospitalization but may jeopardize the participant or may require medical or surgical intervention to prevent one of the other outcomes listed in the above definition. These events should usually be considered serious.

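### Conflicting rules let the same death, ventilation or thromboembolic event be filed as an AE or as expected COVID-19 progression, and only the first reaches the TEAE tables and the AE/SAE-based escalation criteria

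*Protocol*

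**What the plan says.** Three places in the protocol govern how worsening COVID-19 is recorded.

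- **Section 10.3.1.** The list of events that are not AEs includes the disease under study and its "expected progression, signs, or symptoms of the disease/disorder being studied, unless more severe than expected" for that participant.
- **Section 10.3.2.** An event that is not an AE cannot be an SAE "even if serious conditions are met (eg, hospitalization for signs/symptoms of the disease under study, death due to progression of disease". The same section also says, with no exception for the disease under study, "Complications that occur during hospitalization are AEs", and that a complication prolonging the stay is serious.
- **Section 8.3.7.** Under the heading "Disease Related Events and/or Disease Related Outcomes Not Qualifying as AEs or SAEs" the entry is only that it does not apply. Section 8.3.6, "Cardiovascular and Death Events", and Section 8.3.8 on AEs of special interest are marked the same way.

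Safety is the only primary objective (Section 3). Its endpoints are TEAEs, laboratory abnormalities, and changes in vital signs, SpO2 and ECG. SAP Section 3.1.1 flags TEAEs from AEs by their start time.

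**The concern.** The participants are already in hospital with a disease whose complications overlap with the harms one would look for in this drug. Protocol Section 2.2 says that such patients "are at increased risk of developing complications such as severe inflammation associated with elevations in pro-inflammatory cytokines", and goes on to ARDS, cardiac injury, thromboembolic events, hypercoagulability and kidney injury. In the companion healthy-volunteer study, Section 2.2.2.1 describes monitoring "to evaluate any potential pro-inflammatory or hypercoagulable effect of study intervention". In the present study, a history of venous thromboembolism is an exclusion (Section 5.2). The amendment history records that thrombotic events and a worsened pro-inflammatory state were added to the benefit/risk section as possible risks.

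A drug effect that resembles the disease is therefore the kind of event that could be classed as expected progression. That decision comes before causality is considered: Section 10.3.3 requires a causality assessment for each AE or SAE, so an event that never becomes one does not require it. Nor does it require a 24-hour SAE report. The concurrent placebo group exists to separate drug from disease, but the AE tables can only compare events that were recorded.

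**Working it through.** The plan states no figure for this point, so the check is mainly a comparison of rules, followed by an illustration.

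**Step 1. Follow one event through the rules.** Take a participant who starts mechanical ventilation on Day 4 of a Part 2 infusion.

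| Rule applied | Status of the event |
|---|---|
| 10.3.1, judged expected for this participant | Not an AE |
| 10.3.2, consequence of not being an AE | Not an SAE, even if fatal |
| 10.3.1, judged worse than expected | AE; no criterion for the judgement in the visible text |
| 10.3.2, complication during hospitalization | AE, and serious if it prolongs the stay |
| 8.3.7 | Marked not applicable; gives no list of exempt events |

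Two readers of the same protocol can reach opposite answers, each with a section to cite.

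**Step 2. Trace what depends on the answer.**

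- TEAE tables (SAP 3.1.1 and 6.1.1): built from AEs. No visible rule restores an event filed as progression.
- Causality assessment (10.3.3) and SAE reporting (8.3.1.1): apply to AEs and SAEs only.
- Escalation (6.6.1): two criteria count severe nonserious related AEs in 2 participants, or act on a related or unknown-cause SAE in an active participant. The minimum data set for escalation also includes reported SAEs.
- Not dependent on AE status: the laboratory, vital-sign, SpO2 and ECG endpoints (SAP 3.1.2 to 3.1.5); the coagulation, hs-CRP and cytokine summaries (SAP 6.3.2); the 6.6.1 criteria on laboratory, ECG or vital-sign abnormalities, on limits of safety or tolerability, and on other findings; and death as a reason for discontinuation (7.2, tabulated under SAP 6.5.1).

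**Step 3. Scale.** Section 9.2 gives 8 participants per cohort, 6 active and 2 placebo. One uncounted event on active drug is 1/6 = 17% of that arm.

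**Step 4. Illustration only.** Let p be the true per-participant risk on active drug of an event that would qualify for an AE-based rule, and f the share of such events filed as expected progression. Both are assumptions; neither is in the documents. With independent participants, the number recorded among 6 is binomial with probability q = p(1 − f), and

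P(at least 2 recorded) = 1 − (1 − q)^6 − 6q(1 − q)^5.

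For p = 0.20 and f = 0: 1 − 0.8^6 − 6(0.2)(0.8^5) = 1 − 0.262 − 0.393 = 0.345. For f = 0.5, q = 0.10: 1 − 0.531 − 0.354 = 0.114 (before rounding the terms).

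| p | f = 0 | f = 0.25 | f = 0.5 | f = 0.75 | f = 1 |
|---|---|---|---|---|---|
| 0.20 | 0.345 | 0.224 | 0.114 | 0.033 | 0 |
| 0.33 | 0.642 | 0.460 | 0.259 | 0.082 | 0 |
| 0.50 | 0.891 | 0.726 | 0.466 | 0.167 | 0 |

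For a rule that acts on a single event, P(at least 1 recorded) = 1 − (1 − q)^6. At p = 0.20 it falls from 0.738 (f = 0) to 0.469 (f = 0.5).

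**The case against.** Excluding expected disease progression from AEs can be a legitimate choice in a sick population, and the exclusion here is conditional. Several stronger readings that a reader might infer are not supported.

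- **That Section 8.3.7 declares there is no exclusion.** It only marks the heading not applicable, as several neighbouring optional headings are marked. A natural reading is that no study-specific list was set up and Appendix 3 governs. The sections still need to be aligned, but 8.3.7 is not an express denial of 10.3.1.
- **That an investigator's view of severity is the only way back to AE status.** New conditions diagnosed after dosing, laboratory results that need further testing or intervention, and in-hospital complications are also routes in. A new DVT or PE could well enter this way. Because patients who are critically ill, or expected to become so within 24 hours, are excluded, early ventilation would be hard to call expected.
- **That the whole primary endpoint, or all escalation control, is exposed.** Step 2 of the working shows otherwise. The sponsor also reviews safety data unblinded (Section 9.5), and the SAE criterion needs a related or unknown judgement as well as a recorded event.
- **That the drug has been shown to mimic the disease.** The monitoring in Section 2.2.2.1 belongs to the healthy-volunteer study, which reported no evidence of a pro-inflammatory effect.
- **That clinical worsening is nowhere summarized by arm.** Section 4.2 refers to a redacted measure of disease progression, and related exploratory and SAP text is also redacted, so this cannot be asserted. Part of the risk assessment in Section 2.3.1 was also not available for this review.

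Blinded investigators (Section 6.3.1) make differential misfiling less likely. All of these limits stand. They narrow the point but do not settle which rule applies, and none visibly counts a ventilation or thromboembolic event filed as progression in the primary safety analysis. A death would show in disposition, but not as a safety event with a causality assessment.

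**Conclusion.** The point holds in a limited form. The rules conflict, the threshold for worse than expected is undefined in the visible text, and an event filed as expected progression is lost to the TEAE part of the primary endpoint, the required causality assessment and the AE/SAE-based escalation criteria. The other primary safety measurements, the discretionary escalation criteria and the count of deaths in disposition remain.

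The size cannot be derived from the documents. The 17% is the weight of one hypothetical event, and the probabilities above rest on assumed values of p and f and on independence between participants; they show direction and sensitivity, not an expected loss. The conclusion also assumes that the redacted text contains no rule resolving the conflict. In a first-in-human study whose only primary objective is safety, this should be corrected.

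**What to change.** Reconcile Sections 8.3.7, 10.3.1 and 10.3.2 so that one rule applies to COVID-19 progression, and state how worse than expected is to be judged. Whichever reporting route is kept, record all deaths, progression to mechanical ventilation or ECMO, and thromboembolic events, regardless of whether they were judged expected. If the redacted progression measure already captures some of these, use it as the source. Add one by-arm table of these events to the safety analysis in the SAP, and include it in the data reviewed at each escalation step. No dose or stopping criterion needs to change for this.

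The cost is a small CRF addition and one more table. Events after discharge must be asked for at the follow-up contacts, some of which may be by phone. The safety output will contain more disease events, and in each cohort they would be read against only 2 placebo participants, so the table will support review of individual cases more than a comparison of rates.
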